2.1 Background and rationale

Chronic kidney disease (CKD) is defined by an estimated glomerular filtration rate (eGFR) less than 60 mL/min per 1.73 m² or evidence of persistent kidney damage, such as excessive albuminuria. CKD is associated with significant morbidity and mortality but the most important complication of CKD is the progression to kidney failure (end-stage renal disease [ESRD]). Patients who progress to ESRD require dialysis or transplantation to survive. They experience numerous complications, have high mortality rates,¹ and their care is very expensive.² Therefore, preventing or slowing the progression from CKD to ESRD is an important clinical and research goal. Currently, few treatments have been proven to slow progression, and even when these therapies are appropriately applied, many patients still progress to ESRD.³ This may be explained in part by inflammation and fibrosis, two processes that play a role in the progression of CKD,^{4,5} but are not addressed by current therapies.

Curcumin, a component of the dietary spice turmeric, has proven anti-inflammatory and anti-fibrotic properties and has been shown to mitigate renal damage in multiple animal models of CKD.⁶⁻⁹ The ability of curcumin to reduce albuminuria in humans is supported by two trials in patients with nephrotic-range proteinuria.¹⁰⁻¹² However, these trials were small and patients were treated with turmeric, of which curcumin is only a small component. Furthermore, curcumin in its traditional form has very poor bioavailability.¹³⁻¹⁵ To increase patients' exposure to curcumin, we chose to study a micro-particle formulation that is 27 times more bioavailable.¹⁶ Curcumin use has been associated with improved glycemic control in animal models,¹⁷ and human studies.¹⁸

MPAC-CKD-1 is a double-blind, placebo-controlled randomized trial, where patients are followed for 6-months after randomization. The primary goal of the trial is to assess the effect of micro-particle curcumin (versus placebo) on two important biomarkers of CKD progression: albuminuria and eGFR. Positive effects in either of these markers will justify a larger, international trial to determine whether micro-particle curcumin versus placebo decreases the risk of ESRD in patients with CKD.

2.2 Objectives

Our primary objective is to assess the between-group difference in two outcomes examined separately: urinary albumin-to-creatinine ratio (6-month post-randomization value) and change in eGFR from pre-randomization to 6-months post-randomization.

Our secondary objective is to assess: i) the between-group difference in health related quality of life (as assessed by a 6-month change in the RAND version of the 36-Item Short Form Health Survey [SF-36]), ii) the between-group difference in glycemic control (as assessed by a 6-month change in glycated hemoglobin among patients with diabetes mellitus; diabetes mellitus was a stratification variable in the randomization), iii) the risk of a composite outcome of progressive CKD, ESRD or death with micro-particle curcumin versus placebo, and iv) the between-group difference in measured serum levels of curcumin and its major metabolites (to be done on measurements taken 3-months after randomization in the first 30 participants; being done to assess curcumin bioavailability).^{14,16}

We will also conduct a pre-specified exploratory subgroup analysis of the primary outcomes based on a higher or lower estimated risk of future kidney failure (based on the kidney failure risk equation¹⁹).

3. Study Methods

3.1 Trial design

MPAC-CKD-1 is a parallel group, double-blind, placebo-controlled randomized trial. Participants were randomly assigned to receive either microparticle curcumin or matching placebo in a 1:1 ratio. Microparticle curcumin was administered at 90 mg per day (three 30 mg capsules once daily) for 6 months. The dose remained constant over the study period.

3.2 Randomization

Balanced block randomization was conducted using a computerized algorithm with variable block sizes; treatment allocation was stratified by site (3 sites in London, 1 site in Hamilton) and by the presence or absence of baseline diabetes mellitus. After providing written informed consent, patients were allocated randomly by means of a 24-hour online computerized system to maintain allocation concealment. Participants, investigators, and all research staff are unaware of the treatment allocation. Unblinding could have occurred in the setting of a severe adverse reaction in which the treating physician believed the investigational product may have had a role in the patient's condition or treatment. Unblinding events will be summarized by group.

3.3 Sample size

Most physicians would view a 15% to 25% reduction in albuminuria as evidence of a promising treatment effect. Such was the case for angiotensin converting enzyme (ACE) inhibitors and angiotensin receptor blockers (ARBs), which showed a reduction in albuminuria of 15% to 50% and were later proven to reduce the risk of mortality and ESRD.²⁰⁻²³

Heerspink et al.²⁴ conducted a meta-analysis of randomized controlled trials with different types of interventions, including renin-angiotensin-aldosterone (RAAS) inhibitor versus control, and RAAS inhibitor versus calcium-channel blocker. The overall between-group difference in change in log-transformed urine albumin-to-creatinine ratio after 6-months of follow-up was reported as a geometric mean ratio and was estimated using patient-level data. Across all treatment interventions, the estimate of the geometric mean ratio was 0.78, 95% confidence interval (CI) 0.74 to 0.82 (i.e. a lowering of urinary albumin-to-creatinine ratio across treatment groups). Within the same trials, over a median follow-up time of 3.4 years, the active treatment resulted in a lowering of the hazard of the composite progressive CKD endpoint defined by ESRD (chronic dialysis or transplant), doubling of serum creatinine or eGFR < 15 mL/min per 1.73 m² (hazard ratio [HR] 0.73, 95% CI 0.67 to 0.81). The authors estimated that a 30% decrease in geometric mean ratio of 6-month urinary albumin-to-creatinine ratio is associated with an average 27% decrease in the hazard for the clinical outcome. Inker et al.²⁵ conducted a similar meta-analysis of treatment effects in randomized controlled trials to investigate between-group difference in change in eGFR over time as a surrogate endpoint for kidney disease progression. The authors found that the overall mean treatment effect on the total slope over 3 years was 0.45 mL/min per 1.73 m², 95% CI 0.19 to 0.72, comparing treated patients to control arm patients. The active treatment led to a HR of the same composite progressive CKD endpoint of 0.76, 95% CI 0.69 to 0.84. The authors estimate that each 0.75 mL/min per 1.73m² per year greater treatment effect on the total eGFR slope was associated with an average 27% lower hazard for the clinical endpoint.

In our preliminary work on urinary albumin-to-creatinine ratio testing, we found patients eligible for MPAC-CKD-1 had a mean initial urinary albumin-to-creatinine ratio of 128.3 mg/mmol.²⁶ Over 3 months, we observed a mean increase in the urinary albumin-to-creatinine ratio of 30.7 mg/mmol and found the standard deviation of the change to be 69.2 mg/mmol. Enrolling a total of 518 patients and

accounting for 5% loss to follow-up allows for 82% power ($\alpha = 0.025$) to detect a geometric mean ratio of 0.75, assuming a standard deviation of the 6-month log-transformed albumin-to-creatinine ratio of 1.0.²⁷ For the between-group difference in change in eGFR (6-month eGFR minus pre-randomization eGFR), we will have 81% power ($\alpha = 0.025$) to exclude a difference of 1.65 mL/min per 1.73 m² between treatment and control groups (using a standard deviation of the change of 5.8 mL/min per 1.73 m²). In general, the average decline in eGFR in albuminuric CKD patients is 2 to 4 mL/min per 1.73 m² per year (with a standard deviation of 3-4 mL/min per 1.73 m² per year).^{28,29} The standard deviations used in these sample size calculations are based on overall standard deviations observed in the MPAC-CKD-1 study.

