To ensure we can achieve this recruitment goal, we have assessed the number of provisionally eligible patients managed in the 4 clinics involved in this trial and have gauged the success of a recently conducted trial with similar inclusion criteria.^{26,27} In addition, we have worked closely with research

[figure not shown]

Figure 1. Participant timeline.

Note. eGFR = estimated glomerular filtration rate; SF-36 = Short Form-36; UACR = urinary albumin-to-creatinine ratio.

coordinators to remove possible barriers to enrollment and streamline the data collection process.

Data Collection Methods

We will gather outcome measures 3 months and 6 months after randomization. To reduce the variability in the urinary albumin-to-creatinine ratio, we will take the mean of first morning urine samples collected on 2 consecutive days. In our previous work, we determined that the mean of two samples substantially reduced the standard deviation of the log-transformed percentage change from 0.59 to 0.49.²⁸ We will calculate the eGFR rates using the measured plasma creatinine concentrations. These will be measured at central hospital-based laboratories using standardized enzymatic colorimetric methods.

Nonadherence

Patients who miss taking the investigational study medication over 7 or more days during any 4-week period will meet with an investigator to discuss ways of improving adherence. We will catalogue the reasons for nonadherence and the strategies used to overcome them. Patients who do not attend study visits will be contacted and encouraged to comply with the protocol in whatever way they can. Until the study ends or the participant withdraws consent, we will attempt to reach them 3 times within each 4-week period to determine their status. In extenuating circumstances, we will contact the patient's family physician to determine the patient's vital status.

Statistical Methods

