5.4 Withdrawal/follow-up

Participants who stop taking the study drug, but do not withdraw consent to participate in the study, will continue with the study's scheduled telephone visits and may replace remaining in-person visits with telephone visits. Participants wishing to withdraw consent will be asked to complete the closing telephone visit (scheduled for 4 weeks after study drug completion) 4 weeks after withdrawal of consent. The number and percentage of participants who withdraw from the study will be reported overall and by group. Reasons for study withdrawal will be presented in a supplementary document.

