6.1 Outcome definitions and analysis methods

Two primary outcomes

We will assess two outcomes: the between-group difference in 6-month urinary albumin-to-creatinine ratio (log-transformed, measured in mg/mmol), and the 6-month change in eGFR (6-months post-randomization minus pre-randomization, measured in mL/min per 1.73m²). Placebo will serve as the referent group in all analyses.

Albuminuria: Albuminuria will be measured using urinary albumin-to-creatinine ratio from first morning urine samples. At each visit (pre-randomization, and 3- and 6-months post-randomization), urinary albumin-to-creatinine ratio is measured on two consecutive days and the average of the two values will be computed. The average of the two values will be log-transformed using the natural logarithm. A summary of the pre-treatment, 3-month and 6-month urinary albumin-to-creatinine ratio measurements will be provided. The geometric mean ratio of 6-month urinary albumin-to-creatinine ratio will be estimated using linear regression, where the outcome is the log-transformed average of two 6-month follow-up visit urinary albumin-to-creatinine ratio measurements minus log-transformed average of two pre-treatment urinary albumin-to-creatinine ratio measurements, adjusting for a treatment indicator variable and the log-transformed average of two baseline urinary albumin-to-creatinine ratio measurements. The 95% or 97.5% CI for the geometric mean ratio will be presented.³³

eGFR: eGFR will be calculated using the CKD-EPI formula, which includes patient age, sex, race (black vs. other), and the serum creatinine concentration.³⁴ We will summarize the pre-randomization, 3-month and 6-month eGFR measurements by group. We will estimate the between-group difference in change in eGFR (6-month eGFR minus pre-randomization eGFR), expressed in mL/min per 1.73m², using linear regression. The outcome is the change in eGFR (6-month value minus pre-randomization value) and the treatment indicator variable will be included as a covariate. The 95% or 97.5% CI for the between-group difference in change in eGFR will be presented.

Secondary outcomes

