“Using these data, enrolling 250 patients per group will allow an 87% power ($\alpha=0.025$) to exclude a difference of 21 mg/mmol. To allow for loss to follow-up, we expect to recruit up to an additional 75 patients to reach a minimum of 250 patients per arm with complete follow-up data.”	“Enrolling a total of 518 patients and accounting for 5% loss to follow-up allows for 82% power ($\alpha = 0.025$) to detect a geometric mean ratio of 0.75, assuming a standard deviation of the 6-month log-transformed albumin-to-creatinine ratio of 1.0”	We will follow the recently published methods used by Heerspink et al. (Lancet Diabetes Endocrinol. 2019;7:128-39) for between-group comparisons involving albumin-to-creatinine data. These methods were published after the creation of our original protocol. We have updated our sample size calculations to reflect this.
“For changes in eGFR, we will have 90% power ($\alpha = 0.025$) to exclude a difference of 2.3 mL/min/1.73m ² between treatment and control groups (using a standard deviation of 4 mL/min/1.73m ²).”	“For the between-group difference in change in eGFR (6-month eGFR minus pre-randomization eGFR), we will have 81% power ($\alpha = 0.025$) to exclude a difference of 1.65 mL/min per 1.73 m ² between treatment and control groups (using a standard deviation of the change of 5.8 mL/min per 1.73 m ²).”	We have updated our sample size calculations using the overall standard deviation of the change in eGFR in the MPAC-CKD-1 study (without any by-group computations); we have also updated the detectable between-group difference to more closely align with observed effects in Inker et al. (J Am Soc Nephrol. 2019;30:1735-1745).

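### Does the stated 82% power for albuminuria misdescribe the trial, given that the planned analysis adjusts for baseline?

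*Combined protocol and SAP*

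**What the plan says.** SAP section 3.3 starts from "Enrolling a total of 518 patients and" allows for 5% loss to follow-up, and reports 82% power at alpha 0.025 for a geometric mean ratio of 0.75, "assuming a standard deviation of the 6-month log-transformed albumin-to-creatinine ratio of 1.0". It gives the source of that input: "The standard deviations used in these sample size calculations are based on overall standard deviations observed in the MPAC-CKD-1 study". The same section sets the clinical scale: "Most physicians would view a 15% to 25% reduction in albuminuria as evidence of a promising treatment effect".

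Section 6.1 (Albuminuria) plans a linear regression of the change in log UACR from pre-treatment to 6 months, "adjusting for a treatment indicator variable and the log-transformed average of two baseline urinary albumin-to-creatinine ratio measurements". Section 4.1 tests the two primary outcomes by the Hochberg procedure at an overall 0.05. Supplemental Table 1 explains the new power statement by the adoption of a published meta-analysis's methods for UACR, and adds: "We have updated our sample size calculations to reflect this". The SAP gives neither a baseline to 6-month correlation nor a residual standard deviation for log UACR.

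**The concern.** When baseline log UACR is a covariate, precision depends on the residual standard deviation, not on the standard deviation of the 6-month value. The power statement uses the latter, so it describes a simpler comparison than the one planned. The eGFR calculation in the same section shows no such mismatch: it uses the standard deviation of the change, and the eGFR model is an unadjusted comparison of changes. Supplemental Table 1 says the UACR calculation was updated to follow the new method. The update moves to the log scale but has no term for baseline.

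What would be at stake is the reading of a null result. As stated, the design reaches 80% power only at a ratio of 0.757, a 24.3% reduction, which is close to the far end of the range that the SAP calls promising. If the planned analysis is appreciably more precise, a reader who relies on section 3.3 would underrate what the trial could detect.

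**Working it through.** **Inputs.** From SAP section 3.3: 518 enrolled, 5% loss, ratio 0.75, standard deviation 1.0, alpha 0.025; for eGFR, a difference of 1.65 with standard deviation 5.8. From section 3.1: 1:1 allocation. From section 4.1: two-sided tests and the Hochberg rule. The baseline to 6-month correlation r is not in the documents, so any value below is an assumption.

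**Step 1: reproduce the stated power.**
- Per arm: n = 518 × 0.95 / 2 = 246.
- Effect: |ln 0.75| = 0.2877. Standard error: 1.0 × √(2/246) = 0.0902. Ratio of the two: 3.191.
- Power = Φ(3.191 − 2.241) = 82.9% (82.7% with the t distribution), against 82% stated.

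The figure is right for its inputs, as an unadjusted comparison.

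**Step 2: add baseline adjustment.** The residual standard deviation is s = 1.0 × √(1 − r²). It is the same whether the outcome is the 6-month value or the change, because baseline is in the model. Power = Φ(|ln ratio| / (s × 0.0902) − 2.241). The ratio detectable with 80% power is exp(−(2.241 + 0.842) × s × 0.0902).

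| Assumed r | s | Power at 0.75 | Ratio detectable with 80% power |
|---|---|---|---|
| 0 | 1.000 | 82.9% | 0.757 |
| 0.3 | 0.954 | 86.5% | 0.767 |
| 0.5 | 0.866 | 92.6% | 0.786 |
| 0.7 | 0.714 | 98.7% | 0.820 |
| 0.8 | 0.600 | 99.9% | 0.846 |

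Since s cannot exceed 1.0, adjustment cannot lower power, apart from one degree of freedom out of about 490, which is negligible.

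**Step 3: add the Hochberg rule.** UACR is also declared significant when its P value and the eGFR P value are both below 0.05. At r = 0:
- UACR power at alpha 0.05 = Φ(3.191 − 1.960) = 89.1%.
- If the tests are independent, power = 82.9% + (89.1% − 82.9%) × P(eGFR P value below 0.05).
- No eGFR effect: P = 0.05, so power is 83.2%.
- eGFR effect of 1.65: 1.65 / (5.8 × 0.0902) = 3.155 and Φ(3.155 − 1.960) = 88.4%, so power is 82.9% + 6.2% × 0.884 = 88.4%.

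So the planned test exceeds the stated figure even at r = 0. The second gain is as large as that from adjustment with r of about 0.37.

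**Step 4: can r be recovered from the documents?** The protocol's Data Collection Methods report pilot work in which "the mean of two samples substantially reduced the standard deviation of the log-transformed percentage change from 0.59 to 0.49". If the standard deviation were 1.0 at both visits, r = 1 − 0.49²/2 = 0.88 for the mean of two samples. That makes a correlation near zero implausible. It does not fix r, because the figure comes from a pilot, its time interval is not stated there, and equal standard deviations of 1.0 are themselves assumed.

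**The case for a change.** The best case for a change is that the SAP chose to restate power from trial data, so the restated figure ought to belong to its own primary model. The cost is small: one pooled, blinded regression and a sentence or two. The SAP cites a pooled ratio of 0.78 as a benchmark. Power at 0.78 is 69.6% as stated, but 82.7% if r = 0.5 and 94.7% if r = 0.7, so the stated figure makes the trial look weak for an effect that it may be well able to detect. Nor does the SAP tell readers that 82% is a floor. It is one only if the standard deviation is 1.0 and loss is 5%, and section 5.4 says that participants who stop study drug "may replace remaining in-person visits with telephone visits", which could cost urine samples.

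Much of this stands as description: the label is missing and the sentence would be cheap. It does not show harm. Section 3.3 names the standard deviation it uses, so a statistician can see which comparison was powered. Section 5.4 gives no loss rate, and loss and standard deviation are separate planning assumptions that have nothing to do with baseline adjustment. A figure built on residual variance at a fixed alpha would still leave out the Hochberg rule and the multiple imputation in section 6.1, so it too would not be the exact power of the planned test. Once the result is known, the tool for judging a null finding is the adjusted 95% or 97.5% confidence interval that sections 4.1 and 6.1 promise. It carries whatever precision baseline adjustment brings.

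**Conclusion.** No change follows. The 82% is computed correctly from a disclosed input and errs on the safe side. With a standard deviation of 1.0 and 5% loss, the planned analysis has at least that power at a ratio of 0.75: 83.2% to 88.4% from Hochberg alone under independence, and 86.5% to 99.9% at fixed alpha 0.025 for assumed correlations of 0.3 to 0.8. The documents do not supply the correlation needed to choose one replacement figure.

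The type I error, treatment estimate and interval do not depend on the power statement, and the figure no longer sets the size of a trial that already supplied its own standard deviations. Powering on the spread of the outcome and then adjusting for a prognostic baseline is a common conservative simplification. Noting in section 3.3 that the figure is a minimum under its stated assumptions would be a courtesy to readers. It would not alter what the trial does or can conclude.

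### Is the SAP's eGFR target of 1.65 mL/min per 1.73 m² undermined because the slope effects it cites come to much less over 6 months?

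*Combined protocol and SAP*

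**What the plan says.** SAP section 3.3 sets a target for each co-primary outcome and places published benchmarks beside them.

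- **eGFR target.** With an SD of the change of 5.8, the SAP gives 81% power at alpha 0.025 "to exclude a difference of 1.65 mL/min per 1.73 m² between treatment and control groups".
- **Reason for the target.** The protocol used 2.3 with an SD of 4. Supplemental Table 1 gives the SD observed in the trial, without any split by group, as one reason for the change. The other is "we have also updated the detectable between-group difference to more closely align with observed effects in" the slope meta-analysis.
- **eGFR benchmarks.** Section 3.3 reports from that meta-analysis that "the overall mean treatment effect on the total slope over 3 years was 0.45 mL/min per 1.73 m², 95% CI 0.19 to 0.72", and that "each 0.75 mL/min per 1.73m² per year greater treatment effect on the total eGFR slope was associated with an average 27% lower hazard".
- **Expected decline.** In general, "the average decline in eGFR in albuminuric CKD patients is 2 to 4 mL/min per 1.73 m² per year".
- **Albuminuria.** The SAP gives 82% power at alpha 0.025 "to detect a geometric mean ratio of 0.75, assuming a standard deviation of the 6-month log-transformed albumin-to-creatinine ratio of 1.0". Its benchmarks are 6-month ratios: "the estimate of the geometric mean ratio was 0.78, 95% confidence interval (CI) 0.74 to 0.82", and "a 30% decrease in geometric mean ratio of 6-month urinary albumin-to-creatinine ratio is associated with an average 27% decrease in the hazard".

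Section 3.4 makes every comparison a superiority comparison. Section 4.1 applies the Hochberg procedure, and sections 4.1 and 6.1 commit to a 95% or 97.5% confidence interval for the eGFR difference. Section 2.1 lets a positive effect on either marker justify the larger trial.

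**The concern.** The eGFR benchmarks are slopes and the endpoint is a 6-month change. Section 3.3 sets them side by side without converting one to the other. Halving the annual figures leaves effects several times smaller than 1.65, with power barely above the significance level. Set against the general decline of 2 to 4 per year, that is 1 to 2 over 6 months, 1.65 would be 83% to 165% of the whole expected loss.

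Albuminuria does not have this problem: its target of 0.75 lies between its own 6-month benchmarks of 0.78 and 0.70. A reader who sees 82% and 81% next to each other, with both sets of benchmarks tied to a 27% lower hazard, could think the two outcomes equally sensitive to a worthwhile effect. That reader might then take a non-significant eGFR result as evidence against benefit. The verb *exclude*, used where the albuminuria sentence says *detect*, could encourage this.

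**Working it through.** **Inputs.** From SAP 3.3: 518 patients, 5% loss, SD 5.8, target 1.65, alpha 0.025. From 3.1: 1:1 allocation. From 4.1: two-sided tests, with 0.05 available under Hochberg. The 5% loss is stated in the albuminuria sentence; it is assumed to apply to eGFR as well.

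**The plan's own figure.**
- 518 × 0.95 = 492, so 246 per arm.
- SE = 5.8 × √(2/246) = 0.523.
- Power in the benefit direction = Φ(d/SE − z), with z = 2.241 at 0.025 and 1.960 at 0.05.
- At d = 1.65: Φ(3.155 − 2.241) = 82.0% (81.7% with the noncentral t). The SAP's 81% is reproduced.
- Smallest difference with 80% power: 0.523 × (2.241 + 0.842) = 1.61.

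**The slope effects at 6 months.** Section 3.3 prints 0.45 without a per-year unit, and the time course of the effect is not given. Each row below is therefore an assumption.

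| Reading | 6-month effect | Power, 0.025 | Power, 0.05 |
|---|---|---|---|
| 0.45 per year, constant | 0.225 | 3.5% | 6.3% |
| 0.75 per year, constant | 0.375 | 6.4% | 10.7% |
| Upper limit 0.72 per year, constant | 0.36 | 6.0% | 10.2% |
| Full annual 0.45 reached by 6 months | 0.45 | 8.4% | 13.6% |
| Full annual 0.75 reached by 6 months | 0.75 | 21.0% | 30.0% |
| 0.45 accumulated over 3 years | 0.075 | 1.8% | 3.5% |

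These figures count only the benefit tail. Counting both tails, the first two rows become 3.9% and 6.5% at 0.025, and 7.1% and 11.1% at 0.05.

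**Is 1.65 closer than 2.3?** Against 0.375 the ratio falls from 2.3/0.375 = 6.1 to 1.65/0.375 = 4.4. Against 0.225 it falls from 10.2 to 7.3. The target did move towards the cited effects, and it remains several times larger.

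**Could this trial have aimed at the slope effects?** For 80% power at alpha 0.025 it would need about 4,548 per arm for 0.375 and 12,633 per arm for 0.225.

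**Albuminuria for comparison.** SE = √(2/246) = 0.0902. Power at alpha 0.025 is 82.9% at a ratio of 0.75, 69.6% at 0.78 and 95.7% at 0.70. At the observed mean effects (0.78 and 0.45 per year) the comparison is about 70% against 4%. At the increments tied to the 27% lower hazard (0.70 and 0.75 per year) it is about 96% against 6%.

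**What a null eGFR result would show.** The 97.5% interval has half-width 2.241 × 0.523 = 1.17.
- If the true effect is zero, its upper limit falls below 1.65 with probability Φ((1.65 − 1.17)/0.523), about 82%. For 1.65 itself, *exclude* is a fair description.
- The same interval still contains 0.375 in about 93% of trials, and anyone reading the interval will see that.

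**The case for a change.** The strongest case for a change is that a stated reason should stand up. Being 4.4 times a benchmark instead of 6.1 times is not alignment in any useful sense, and no reading of the printed slopes brings power near 81%; the most generous gives 21%, or 30% at alpha 0.05. The SAP matched the scale of benchmark and endpoint for albuminuria but not for eGFR, and correcting this would cost a few sentences.

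Much of this stands. The conversion is missing, and a reader is helped by knowing it. Three things limit its weight.

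- The SAP claims only that the target moved closer, which is true. It already calls 1.65 a detectable difference and says its SDs come from the trial.
- The 0.75 per year figure is the increment in a regression on hazard. It is not an observed mean effect, so it is not plainly among the effects that Supplemental Table 1 refers to.
- The 4% to 6% figures need a per-year reading of 0.45 and a constant effect. The documents give nothing on an early eGFR effect, which could make the 6-month difference larger or smaller.

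On misreading a null result, the plan has no futility, equivalence or no-effect rule for eGFR. A non-significant eGFR result triggers nothing by itself.

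**Conclusion.** The scale mismatch in the rationale is genuine, but it does not call for a change. The power statement is correct for the difference it names: 82% recalculated against 81% stated. Low power at effects the plan never set out to detect is a limit of a 6-month trial with 246 evaluable patients per arm; it is not an error in the calculation. Reaching those effects would take thousands of patients per arm, and the trial's stated purpose is to decide whether a larger one is justified.

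The SAP describes randomisation as already done and uses the trial's own SDs, so the target no longer drives recruitment. Rewording the reason would leave the sample size, model, alpha, Hochberg procedure, intervals and decision rule as they are. The choice between *exclude* and *detect* is carried over from the protocol's sample-size wording, and sections 3.4 and 4.1 leave no doubt about the test.

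A reader should keep in mind that, with 0.45 read as per year and a constant effect, the cited slopes equal about 0.23 and 0.38 at 6 months. Power for them is about 4% and 6% at alpha 0.025 (6% and 11% at 0.05, benefit tail), and the other readings span about 2% to 30%. The planned confidence interval conveys this when the result is reported.
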